#### 9.4.2.2 Ease of handling questions

For all patients, the ease of handling of the re-usable Respimat SMI will be completed at the time of follow-up assessment, using a set of individual questions with answers to each question scored on a 7-point ordinal scale, with divisions from very dissatisfied to very satisfied (see [Table 4](#) for details).

#### 9.4.2.3 Question on patient preference for re-usable or disposable in Respimat SMI-experienced patients

A single question will be asked only to the Respimat-experienced patients switching from a disposable to a re-usable Respimat SMI product at study entry, to determine their preference

for the type of Respimat SMI: re-usable vs the disposable Respimat SMI (see Table 4 for details).

Table 4: Ease of handling questions and patient preference (for Respimat SMI-experienced patients switching from disposable to re-usable Respimat SMI at the time of study entry)

For all patients		Scoring
Ease of handling	
Q1: How satisfied are you with the ease of removing the clear base?
 
Q2: How satisfied are you with the grip of the cartridge?
 
Q3: How satisfied are you with inserting a new cartridge?
 
Q4: How satisfied are you with the readability of the dose indicator?
 
Q5: How satisfied are you with recognising when you need to replace the cartridge?
 
Q6: How satisfied are you with automatic detachment of the clear base when the cartridge is empty?
 
Q7: How satisfied are you with automatic return to the start-use position when replacing the clear base?
 
Q8: How satisfied are you with the overall ease of handling the inhaler?
 
Q9: How satisfied are you with the sustainability (eco-friendly) concept of the inhaler, due to re-use ability?
 
Q10: How satisfied are you with recognising when to replace the inhaler?
	
All items scored on a 7-point Likert scale:
 
1 = Very dissatisfied          2 = Dissatisfied          3 = Somewhat dissatisfied          4 = Neither satisfied nor dissatisfied          5 = Somewhat satisfied          6 = Satisfied          7 = Very satisfied
 
1 = Very dissatisfied          2 = Dissatisfied          3 = Somewhat dissatisfied          4 = Neither satisfied nor dissatisfied          5 = Somewhat satisfied          6 = Satisfied          7 = Very satisfied          8 = Not applicable

Only for Respimat SMI-Experienced patients switching from disposable to re-usable Respimat SMI at the time of study entry		
Rating of inhaler preference	Q1: Comparing the re-usable with disposable inhaler, please indicate which inhaler do you prefer to use?	
 
- Re-usable inhaler
 
- Disposable inhaler
 
- No preference
 

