## **9.6 DATA MANAGEMENT**

A data management plan (DMP) will be created to describe all functions, processes, and specifications for data collection, cleaning and validation. All data will be collected and entered directly into the electronic data capture (EDC) system.

All participating sites will have access to the data entered regarding the individual site of its own enrolled patients. All sites will be fully trained on using the online data capture system, including the eCRF completion guidelines and help files. Sites will be responsible for entering extracted patient data into a secure internet-based EDC registry database via the eCRF. For electronic patient reported outcomes (ePROs), the data entered by the patients will be directly captured into the EDC.

The eCRFs will include programmable edits to obtain immediate feedback if data are missing (also negative answers, unknown), out of range, illogical or potentially erroneous. These rules may encompass simple checks such as range validation or presence/absence of data. Concurrent manual data review may be performed based on parameters dictated by the DMP.

High data quality standards will be maintained, and processes and procedures utilised to repeatedly ensure that the data are as clean and accurate as possible when presented for analysis. Data quality will be enhanced through a series of programmed data quality checks that automatically detect out of range or anomalous data.

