9.2 Rules for Reporting Statistics

Continuous variables will be summarised using descriptive statistics, i.e., number of non-missing and missing observations, mean, SD, first quartile (Q1), median, third quartile (Q3), minimum and maximum. Whenever applicable, two-sided 95% CIs will be calculated for the difference of means.

For reporting conventions:

- The number of non-missing and missing observations will be presented as whole numbers.

Document: \\\\ .net\\Enterprise\\Sites\\USCBG\\Depts\\BioStat\\Boehringer\\Documentation\\SAP\\Final

Author: _____ Version Number: _____

10

Version Date:

100CT2019

Template No.: RWI_TP_BIOS0013 Revision 1

Reference: RWI WI BIOS0015

Effective Date: 15-Jun-2018

- The minimum and maximum will be presented with the same number of decimal places as in the raw data.
- The mean, median, Q1 and Q3 will generally be displayed with one more decimal place than the raw data.
- The SD will generally be displayed with two more decimal places than the raw data. If there is only one observation (n=1), the SD will be displayed as a hyphen ("--"). If there is no observation, summary statistics will be displayed with a hyphen ("--").

Qualitative variables will be summarised by frequency counts (n) and percentages (%). Percentages will not include the missing category and are calculated over the number of patients with available (non-missing) data. Counts of missing data will be provided in the tables for information only. Wherever applicable, 95% CIs will also be presented.

For reporting conventions, percentages will be reported to one decimal place unless greater precision is deemed appropriate, except for cases when 100% is presented. In cases of a count of 0, the percentage will not be presented.

P-values will be rounded to three decimal places. P-values rounded to less than 0.001 will be reported as <0.001 in tables. P-values greater than 0.999 will be reported as >0.999.

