9.3 Missing Data

Due to the nature of the study, there will likely be missing data (data that are not collected or documented in the patient medical record).

Document:	\	.net\Enterprise\Sites\USCBG\Depts\BioStat\Boehringer\Documentation\SAP\Final
Author:		Version Number: 1.0

Template No.: RWI_TP_BIOS0013 Revision 1 Reference: RWI_WI_BIOS0015

Effective Date: 15Jun2018

Unless otherwise specified in this SAP, all data will be evaluated as reported and no imputation for missing values will be done, except for dates and PASAPQ data. Handling of partial dates and PASAPQ data is described in [Appendix 2](#) and [Section 20.1.2](#), respectively.

Missingness for all variables will be indicated in descriptive tables. In all listings, imputed values will not be presented, however, all variables derived based on imputed values will be flagged.

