20.2.1.3 Re-usable Respimat® SMI Ease of Handling

Analysis Set: FAS

The secondary analysis to evaluate the ease of handling of re-usable Respimat® SMI used in the study will be performed overall and by patient cohort.

Ease of handling will be accessed using a set of individual items with answers ranging from 1 (very dissatisfied) to 7 (very satisfied) and will be collected from the “Ease of Handling (ePRO)” or “Ease of Handling (Paper)” eCRF pages.

The following ease of handling of re-usable Respimat® SMI items will be summarised using descriptive statistics for categorical variables:

- Q1: How satisfied are you with the ease of removing the clear base?
- Q2: How satisfied are you with the grip of the cartridge?
- Q3: How satisfied are you with inserting a new cartridge?
- Q4: How satisfied are you with the readability of the dose indicator?
- Q5: How satisfied are you with recognising when you need to replace the cartridge?
- Q6: How satisfied are you with automatic detachment of the clear base when the cartridge is empty?
- Q7: How satisfied are you with automatic return to the start-use position when replacing the clear base?
- Q8: How satisfied are you with the overall ease of handling the inhaler?
- Q9: How satisfied are you with the sustainability (eco-friendly) concept of the inhaler, due to re-use ability?

Document: \\ .net\Enterprise\Sites\USCBG\Depts\BioStat\Boehringer\Documentation\SAP\Final

Author: Version Number: 1.0
Version Date: 100CT2019

Template No.: RWI_TP_BIOS0013 Revision 1

Reference: RWI_WI_BIOS0015

Effective Date: 15Jun2018

- Q10: How satisfied are you with recognising when to replace the inhaler?

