20.2.1.4 Total PASAPQ Score

Analysis Set: FAS

The total PASAPQ score at study entry (baseline visit) and study end (follow-up assessment) will be summarised using descriptive statistics for continuous variables for the subgroup of Respimat® SMI-experienced patients switching from a disposable to a re-usable Respimat® SMI at study entry.

The absolute change from baseline in total PASAPQ score will also be summarised at study end and will be examined using a two-tailed t-test for paired samples or an appropriate non-parametric test (e.g. Wilcoxon signed ranks test), depending on the distributions of the count/score data. The 95% CI for the difference of the means of the total PASAPQ score will also be presented.

Same analysis will be performed for performance and convenience PASAPQ scores.

Derivations:

- *Absolute change of total PASAPQ score = (Total PASAPQ score at follow-up assessment – Total PASAPQ score at baseline visit).*
- *Absolute change of performance score = (Performance score at follow-up assessment – Performance score at baseline visit).*

Document:	\	.net\Enterprise\Sites\USCBG\Depts\BioStat\Boehringer\Documentation\SAP\Final
Author:		Version Number: 1.0

Template No.: RWI_TP_BIOS0013 Revision 1

Reference: RWI_WI_BIOS0015

Effective Date: 15Jun2018

- *Absolute change of convenience score = (Convenience score at follow-up assessment – Convenience score at baseline visit).*

20.2.1.5 *Respimat® SMI Preference*

Analysis Set: FAS

The secondary analysis to determine the preference for re-usable or disposable Respimat® SMI will be performed for Respimat® SMI-experienced patients switching from a disposable to a re-usable Respimat® SMI at study entry.

The preference for the disposable or re-usable Respimat® SMI will be collected by a single question collected in the “Patient Preference (ePRO)” or “Patient Preference (Paper)” eCRF pages. The following will be summarised using descriptive statistics for categorical variables:

- Q1: Comparing the re-usable with disposable inhaler, please indicate which inhaler do you prefer to use?: Re-usable inhaler, Disposable inhaler, No preference.

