23.5 APPENDIX 4. Ease of Handling Questions and Patient Preference

For all patients, the ease of handling of the re-usable Respimat® SMI will be completed at the time of follow-up assessment, using a set of individual questions with answers to each question scored on a 7-point ordinal scale, with divisions from 1 = very dissatisfied to 7 = very satisfied.

A single question will be asked only to the Respimat® SMI-experienced patients switching from a disposable to a re-usable Respimat® SMI product at study entry, to determine their preference for the type of Respimat® SMI: re-usable vs the disposable Respimat® SMI ([Table 6](#)).

Table 6 Ease of handling questions and patient preference

For all patients		Scoring
Ease of handling	Q1: How satisfied are you with the ease of removing the clear base?	Items scored on a 7-point Likert scale: 1 = Very dissatisfied 2 = Dissatisfied 3 = Somewhat dissatisfied 4 = Neither satisfied nor dissatisfied 5 = Somewhat satisfied 6 = Satisfied 7 = Very satisfied
	Q2: How satisfied are you with the grip of the cartridge?	
	Q3: How satisfied are you with inserting a new cartridge?	
	Q4: How satisfied are you with the readability of the dose indicator?	
	Q5: How satisfied are you with recognising when you need to replace the cartridge?	
	Q6: How satisfied are you with automatic detachment of the clear base when the cartridge is empty?	
	Q7: How satisfied are you with automatic return to the start-use position when replacing the clear base?	
	Q8: How satisfied are you with the overall ease of handling the inhaler?	
	Q9: How satisfied are you with the sustainability (eco-friendly) concept of the inhaler, due to re-use ability?	
	Q10: How satisfied are you with recognising when to replace the inhaler?	

Only for Respimat® SMI-Experienced patients switching from disposable to re-usable Respimat® SMI at the

Document:	\	.net\Enterprise\Sites\USCBG\Depts\BioStat\Boehringer\Documentation\SAP\Final	
Author:		Version Number:	1.0
		Version Date:	100CT2019

Template No.: RWI_TP_BIOS0013 Revision 1

Reference: RWI_WI_BIOS0015

Effective Date: 15Jun2018

Rating of inhaler preference	For all patients	Scoring
	time of study entry	
	Q1: Comparing the re-usable with disposable inhaler, please indicate which inhaler do you prefer to use?	
 - Re-usable inhaler - Disposable inhaler - No preference

Document: \\ .net\Enterprise\Sites\USCBG\Depts\BioStat\Boehringer\Documentation\SAP\Final

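### Does the not-applicable code in Protocol Table 4, which the SAP never mentions, distort the ease-of-handling percentages?

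*Protocol*

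**What the plan says.** Ease of handling is secondary objective 2. It is measured by ten questions at follow-up and reported overall and by cohort.

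The documents describe the response scale in four places:

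- Protocol 9.4.2.2: "answers to each question scored on a 7-point ordinal scale, with divisions from very dissatisfied to very satisfied".
- Protocol Table 4 (under 9.4.2.3): one block running from 1 to 7, then a second block running from 1 to 7 and adding "8 = Not applicable". The table as extracted does not show which question or questions the second block belongs to.
- SAP 20.2.1.3: "answers ranging from 1 (very dissatisfied) to 7 (very satisfied"), with all ten questions listed beneath and a categorical summary specified.
- SAP Appendix 4: "scored on a 7-point ordinal scale, with divisions from 1 = very dissatisfied to 7 = very satisfied". Its Table 6 has a single block from 1 to 7.

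Two general rules would govern an 8 if one were recorded. SAP 9.3 says "all data will be evaluated as reported and no imputation for missing values will be done, except for dates and PASAPQ data". SAP 9.2 says "Percentages will not include the missing category and are calculated over the number of patients with available (non-missing) data". SAP 20.2.2 covers missing data for the PASAPQ domain scores only. SAP 4.3 records no changes from the protocol.

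**The concern.** The protocol offers an answer that the SAP does not list, and the SAP's general rules seem to decide its fate by accident. A ticked 8 has been collected, so it is not missing. It would therefore sit in the denominator of every rating percentage for that item although the patient gave no rating. The contrast with the preference question makes the omission look like an oversight, because there SAP 20.2.1.5 does list the neutral answer: "Re-usable inhaler, Disposable inhaler, No preference".

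A second route leads the opposite way. Protocol 9.6 relies on "a series of programmed data quality checks that automatically detect out of range or anomalous data". If a limit of 1 to 7 were programmed, an 8 could be turned into a missing value and would look like non-response.

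Patients may well use the code. Question 10 asks about knowing when to replace the inhaler, the device takes up to 6 cartridges (Protocol 7), and follow-up lasts about 4-6 weeks. Patients already on the re-usable inhaler (subgroup 1a) have had longer experience of it than switchers or naïve patients. The share answering 8 could therefore differ between the groups shown side by side, and equal ratings could be printed as unequal percentages.

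**Working it through.** The plan states no figure on this point, so there is nothing of its own to reproduce. The check has two parts: how large the literal reading could make the effect, and whether the resulting table would be wrong.

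**Inputs**

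- Enrolment 250 and 10% without evaluable data (Protocol 9.5): 250 × 0.90 = 225 respondents.
- Share answering 8, written *a*: not in the documents. Assumed at 5%, 10% and 25%.
- Share of raters choosing a given category: assumed at 40%.
- Exact Clopper-Pearson intervals, the method named in SAP 9.1.

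**Identity.** With 8 kept in the denominator, printed % = rater % × (1 − *a*).

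| Assumed *a* | Rater % | Printed % with 8 kept |
|---|---|---|
| 5% | 40 | 40 × 0.95 = 38 |
| 10% | 40 | 40 × 0.90 = 36 |
| 25% | 40 | 40 × 0.75 = 30 |

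**In whole patients at 25%.** 0.25 × 225 ≈ 56 answer 8, leaving 225 − 56 = 169 raters. 40% of 169 ≈ 68 choose the category.

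- 8 kept: 68/225 = 30.2% (95% CI 24.3 to 36.7).
- 8 removed: 68/169 = 40.2% (95% CI 32.8 to 48.0).
- 8 treated as missing: the percentage is again 40.2%, but the missing count rises from 25 to 25 + 56 = 81 of 250, that is from 10% to 32.4%.

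**Between cohorts.** With 40% of raters in both, but *a* = 5% in one cohort and 25% in the other, the table prints 38% and 30%. The gap is 8 points with no difference in ratings.

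**Would such a table mislead?** Take the possible treatments in turn.

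1. *8 printed as its own row.* The table shows 68, 56 and 225. The reader gets 68/(225 − 56) = 68/169 = 40.2%, and the exact interval follows from the same two counts. The unequal shares behind the 8-point gap appear in the same table. The SAP already prints non-informative answers as ordinary categories elsewhere: a not-applicable entry for race (12.1), and unknown or not-assessed entries for symptom severity (12.4).
2. *8 set to missing.* The percentages are those among raters. SAP 9.2 requires missing counts in the tables, so the affected item would show 81 missing where other items on the same form show about 25.
3. *8 averaged as a score better than 7.* This would be a real error. Protocol 9.7.1.2 leaves room for a continuous summary, but SAP 20.2.1.3 fixes a categorical one and so closes that route.

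**When would the code be noticed?** SAP 5.2 schedules a dry run of the tables and a data review meeting before lock. A value outside the listed categories would be expected to surface there.

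**The case for a change.** The strongest case for a change is that a SAP should not leave two programmers free to produce different tables for a stated secondary objective, and this one does. The literal reading of SAP 9.2 and 9.3 is sound. The exclusion of uninformative categories in SAP 9.4 concerns subgroups, not item answers. SAP 4.3 does not record the code as dropped. The remedy would be two or three lines before lock, with no effect on data collection.

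Much of this stands. The mismatch is real, the arithmetic is right, and the SAP is silent on code 8. What does not stand is the step from silence to a distorted result. Dilution is inferred from general rules that were not written with this code in mind. SAP 20.2.1.3 and Table 6, the more specific passages, provide no category for 8, so they do not direct an analyst to keep it among the ratings either. SAP 4.3 does not settle whether the code survives, because its table covers major changes to statistical methods and a response option need not count as one. The SAP was written against case form version 2.0 of 23 July 2019, later than the protocol of 11 June 2019, and the table shells are a separate document (SAP 10). Neither was available for this review. If the form dropped the option, no 8 can be recorded.

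The point about confidence intervals is weak, since SAP 20.2.1.3 names none for these items and SAP 9.1 and 9.2 provide them only where applicable. The data-check route is conjecture: Protocol 9.6 describes generic checks and does not say that a limit of 7 would be set on a form that offers 8.

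**Conclusion.** No change to the plan follows. The documents disagree on whether at least one of the ten ease-of-handling items has a not-applicable answer, and the SAP does not say how to tabulate it. That is an unwritten convention which analysts will fill sensibly when they meet the code, either by printing its row or by leaving it out of the denominator. Both give a correct descriptive table when the counts are shown.

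The size depends wholly on an unknown share. Under the literal reading, the loss on a 40% category is 2 points at an assumed 5% answering 8, 4 points at 10% and 10 points at 25%. The 8-point gap between cohorts needs an assumed split of 5% against 25%. With no 8s recorded there is no effect.

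The reach is narrow: one or more items of a sponsor-designed questionnaire (Protocol 9.9), summarised descriptively with no test planned for these items. The PASAPQ total score, its domain scores and the paired comparison in switchers do not use these answers. The conclusion assumes that counts are printed alongside percentages, as SAP 9.2 requires, and that the summary stays categorical, as SAP 20.2.1.3 specifies.

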### **9.4.3 Adverse events**

The safety data including serious and non-serious ADRs, AEs with a fatal outcome and other reportable safety events (see [Table 6](#) and [Section 10.2](#) for further details) will be extracted from the medical records and/or collected from a telephone interview (held by the Investigator's staff) at the time of the follow-up assessment and entered into the eCRF where it will be coded using the Medical Dictionary for Regulatory Activities (MedDRA) and grouped by system organ class (SOC) and preferred term (PT).

## **9.5 STUDY SIZE**

The primary objective of this study is to assess patient satisfaction for the re-usable Respimat SMI, measured by the total mean score of PASAPQ. Assuming a population standard deviation (SD) of 18 points, and a 95% confidence interval (CI), a sample size of at least 50 patients will enable the estimation of a population mean total PASAPQ score within a margin of error (precision) of  $\pm 5.0$  points. Assuming that 10% of patients will not have evaluable data (i.e. loss to follow-up), a total number of 56 patients is required.

To test for differences in the mean total PASAPQ score in Respimat SMI-experienced patients switching from a disposable to a re-usable Respimat SMI product at study entry, the minimum clinically important difference for PASAPQ, which has been previously reported as 8-10 points, will be used ([Hodder and Price 2009](#)). A sample size of 56 patients will have a 90% power to detect a minimum 8-point difference in total PASAPQ score means assuming SD of differences of 18 points, using a paired t-test with a 5% two-sided significance level. To account for potential 10% of patients with no evaluable data, a total sample size of minimum 63 patients is required. If the difference in the mean total PASAPQ score is further reduced to 6 points, the sample size will increase to 107 patients, accounting for a potential 10% patients with no evaluable data at follow-up assessment. Different scenarios, depending on the desired power (80% or 90%) and mean difference of total PASAPQ score (6-, 8- and 10-point difference) and considering an 18-point SD of differences are presented in Table 5.

Table 5: Sample size scenarios for detecting difference in total PASAPQ score means

	Scenario 1	Scenario 2	Scenario 3	Scenario 4	Scenario 5	Scenario 6
Significance level ( $\alpha$ )	0.05	0.05	0.05	0.05	0.05	0.05
Mean difference of total PASAPQ score	6	6	8	8	10	10
SD of differences	18	18	18	18	18	18
Power (%)	80	90	80	90	80	90
Sample size, n	73	97	42	56	28	37

In this study, a total of 250 patients will be enrolled, which is adequate to meet the primary and the secondary outcomes of the study. Further, subgroup analyses will be performed only if the subgroups of interest include more than 20% of all patients.

